12 WITHDRAWAL CRITERIA

A participant may, at any time, withdraw from the study without giving a reason, and without it affecting his/her clinical care. Participants will be asked to give a reason for withdrawal from the study but do not have to provide one. Participants who wish to withdraw will be given the option to continue with partial follow-up, e.g. provide primary outcome data only, to minimise data loss. Participants who withdraw from the study will not be replaced. The CTU data management team will ensure that participants who formally withdraw from the study are not contacted for any subsequent follow-up data collection (aside from any partial follow-up arrangements made with individual participants). Data collected prior to withdrawal will be included in the study analysis unless a participant specifically requests that their data are removed from the database. If a participant withdraws for the study they will not be replaced.

13 COMPLIANCE

Appointments will be arranged at times and places to suit the participant. Up to two reminder letters, and a follow-up phone call will be made to participants if they don't return the accelerometer. Up to two reminder letters will be issued to remind participants to return the questionnaire booklets, and the option of the participant telephoning a member of the research team to aid completion of the questionnaire booklets will be offered. A shopping voucher will be mailed to participants upon CTU receipt of the completed baseline, 3, 9 and 15 month questionnaire booklets. Motivational postcards may be mailed to participants ahead of the 3, 9 and 15 month follow-up assessments being sent out to increase response rates.

14 ETHICAL CONSIDERATIONS

14.1 Risks to participants

Moderate intensity physical activity is safe and is recommended for most adults. It is anticipated that most smokers will increase walking, and walking has no contraindications for most. Other physical activities will also be offered in the community, and participants will be advised on the suitability of these.

14.2 Protection against risks

During the screening process those smokers who are contraindicated for moderate intensity physical activity, or who have injury or illness which might be aggravated by exercise, will be required to gain approval from their GP before engaging in the study. Vigorous intensity activity can acutely and transiently increase the risk of sudden cardiac death and acute myocardial infarction in susceptible persons, so the focus of all recommendations for increasing PA will be on moderate intensity PA. Participants will be given clear guidance on exercising at this intensity (ie, something that increases the heart and breathing rate but not to the point of breathlessness or unable to maintain a conversation). Participants will be advised to seek approval from their GP prior to engaging in any vigorous intensity PA, regardless of age and gender. The smokers will be monitored for contraindications to exercise, for adverse events including physical symptoms (e.g. chest pain, extreme breathlessness), or change in health status at each counselling session.

All study personnel will be asked to comply with their employers lone working policy. All staff working with study participants will be required to complete Disclosure and Barring Service (DBS) checks, as they may be working with vulnerable individuals.

14.3 Potential benefits of the proposed research

The smokers participating in the study may have a greater chance of stopping smoking and remaining abstinent, relative to those who receive usual care. We may expect that those in the exercise intervention will have an enhanced opportunity of stopping smoking. Those who increase and maintain regular physical activity during and following the study will receive many general health benefits, including a reduced risk of developing cardiovascular disease, stroke, hypertension, obesity and some cancers, even if they continue smoking [60].

14.4 Importance of the study knowledge to be gained

Little is known about if and how behavioural support can help smokers to cut down, and if cutting down then leads to more quit attempts and continuous abstinence. If the physical activity intervention is shown to be effective and cost-effective for increasing quit attempts and smoking cessation it will offer important evidence for the design of behavioural interventions which are not currently available in the NHS. Smokers are typically less active than the general population, [58] and evidence from interventions that help change multiple health behaviours are urgently required. Weight gain is common among quitters [62, 38], but nothing is known about the effects of smoking reduction on weight gain or weight concern. This study may provide unique information on changes in a variety of psychological variables (eg, cravings and withdrawal symptoms) and weight gain and weight concerns among those who cut down and quit.

15 SAFETY REPORTING

15.1 Definitions:

15.1.1 Adverse event (AE)

Any untoward medical occurrence, unintended disease or injury or any untoward clinical signs in study participants whether or not related to any research procedures or to the intervention.

15.1.2 Serious adverse Event (SAE)

A serious adverse event in the context of this study is any untoward medical occurrence that:

- Results in death
- Is immediately life-threatening
- Requires inpatient hospitalisation
- Results in persistent or significant disability/incapacity

When an AE occurs, the responsible investigator must assess whether the event is classified as serious (i.e. an SAE).

15.1.3 Reporting requirements for this study

The recording and reporting of non-serious AEs in this study is not required. SAEs will be reported from the time of consent until 4 months after the last trial intervention. If an unreported event from this time period is identified at a later date, retrospective reporting must occur immediately. Events occurring outside of this time period may still be reported if the Investigator feels that it is medically important. Information about SAEs may be captured in a variety of ways (see below). SAE report forms will be returned to the CTU, and entered into the study database. The Trial Office is responsible for reporting relevant events to the Sponsor, and ethics committee within required timelines in accordance with trial procedures and regulatory requirements. The PI is responsible for reporting events to local parties, in accordance with local practice. All reportable events and any others as advised by the main REC, will be sent to Investigators for submission to relevant parties in accordance with local practice. Trial staff will send a safety report to the main REC, and to the Sponsor annually. Sites should distribute this report in accordance with local practice and regulatory requirements.

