8.8 Randomisation

Participants will be individually randomised to either the intervention, or control group (1:1 ratio) following consent, and completion of baseline assessments, to ensure concealment is preserved. Randomisation will be achieved by means of a 24-hour web-based system created by the Peninsula Clinical Trials Unit (CTU) in conjunction with a statistician independent from the trial team, and will use random permuted blocks, with stratification for recruitment site, and a dichotomised low/high score from HSI. The randomisation website will incorporate a brief online case report form (CRF) that, when required details have been completed, will allow randomisation. The CTU programming team will run checks before and during the trial to verify the integrity of the randomisation system.

It is not possible to blind participants to their allocated group. Every effort will be made to ensure that the trial team (including the researcher who is collecting follow-up CO measures at each site), remain blind to the allocation of each participant when collecting follow-up data. It is possible that participants will disclose if they have received support to reduce smoking prior to such an appointment. Health trainers delivering the intervention will also obviously be aware of the participant's allocation to trial arm, and they will be discouraged from communicating with site researchers about this. Questionnaire booklets and accelerometers will be mailed out from and returned to the CTU without knowledge of the trial arm allocation.

Following randomisation all participants will be sent a letter from CTU confirming which trial arm they have been assigned to, and a guidance sheet on usual support locally for smoking reduction and cessation. The participants GP will also be sent a letter notifying them that one of their patients is participating in the study.

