9 INTERVENTION

9.1 TARS Intervention

Participants in the intervention arm will be offered open-ended support from a Health Trainer (HT) which will broadly include the content described in Table 1 below. In the interests of ensuring it meets the participants needs the HT will suggest options for the support provided but empower the participant to decide what support is offered, where and when. In the pilot EARS trial participants had an average 4.2 sessions by phone or face to face with the HT with a range of 0-8 [1]. If a smoker wishes to quit at any time during the 8 week intervention period, they will be offered 6 weeks of additional behavioural and motivational support from the HT, as well as support to access services as part of usual care to stop smoking (as available at each location) if desired. If a smoker wishes to reduce smoking using e-cigarettes or licenced nicotine containing products (LNCP) they will also be offered any local available support for this. Typically, there are no formal programmes for use of medication during reduction and people usually buy their own NRT or, more often, e-cigarette or vaper product. We will also monitor any national guidelines (eg, NICE PH45 guidelines for smoking harm reduction) for any changes and adopt our actions and guidance accordingly throughout the trial.

The goal of the intervention is to promote motivation to make a quit attempt. If a smoker wishes to quit at any time during the 8 week intervention period, they will be recommended to attend a stop

smoking service, where they will be offered and pharmacological and behavioural support that comprises usual smoking cessation practice. If the participant prefers, the health trainer could continue to provide cessation support and recommend options for use of pharmacotherapy.

Intervention components	Aim	Content	Process and outcome evaluation
Active participant involvement (1)	Develop rapport, build trust, and shared respect.	Effective communication skills. Build autonomous support.	Participant feedback on HT-led support.

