9.2 Support as usual

Participants allocated to both arms of the trial will receive guidance for smoking reduction and cessation, including web links to what is offered at local level, or paper versions of this information. In the current financial climate and without clear evidence of benefit and a clear pathway of care, it

is unlikely that there will be much support for smoking reduction as described as usual care. Given the rapidly changing public health environment we do not propose to request approval for this guidance or amendments from the REC if and when changes occur to what is offered locally to prevent unnecessary delays to the trial but will be happy to forward versions as appropriate.

10 Follow-up Assessments – all participants

10.1 3 month follow-up assessments

The 3 month assessments will be mailed to participants in the form of a questionnaire booklet, with a cover letter, and freepost return envelope. An opportunity will be given for participants to complete the questionnaire booklet over the telephone with a member of the local research team if they would prefer. A subset of study participants will also receive an accelerometer by post, and instruction sheet at the 3 month time point.

The 3 month questionnaire booklet contains questions relating to the following:

- Smoking behaviour
- Importance and confidence in smoking reduction and cessation
- Importance and confidence in being physically active
- Availability of support to reduce smoking and increase physical activity
- Use of physical activity for smoking regulation
- Self-reported physical activity (7-day physical activity recall)
- Planning to change smoking
- · Planning to change physical activity
- Self-monitoring of smoking
- · Self-monitoring of physical activity
- Urge & strength of urge to smoke
- Use of e-cigarettes and NRT (nicotine replacement therapy) products
- Health related quality of life (EQ-5D-5L & SF12)
- Physical activity (accelerometer) (7 days)
- Self-reported height and weight (BMI)
- Health service utilisation and costs, including smoking related costs
- Serious adverse event reporting

Participants who self-report that they have quit will be invited to attend a face-to-face assessment, which will include the following additional assessments:

- Self-reported prolonged abstinence (since last quit attempt, with date, if relevant)
- Expired carbon monoxide (CO) measurement

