15.2 Serious adverse event self- reporting at 3 and 9 months

The questions in the self-completion study questionnaire booklets ask participants to record the number of in-patient episodes within a set recall period. At the 3 and 9 month time points, participants are asked to record if they have been hospitalised, the reason for any hospital admission during the past three and six months respectively and whether they think that the hospitalisation was related to participation in this study. On receipt of a questionnaire indicating a past hospital admission, the CTU will liaise with the relevant local RA who will be responsible for ascertaining further details about the SAE from the participant and/or GP records as appropriate.

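### The SAE reporting window in Protocol section 15.1.3 has no defined end for controls, varies within the intervention arm, and does not match the month 0–9 SAE collection in sections 15.2 and 10.6

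*Protocol*

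**What the plan says.** Section 15.1.3 sets the only reporting period: "SAEs will be reported from the time of consent until 4 months after the last trial intervention". It adds that "Events occurring outside of this time period may still be reported if the Investigator feels that it is medically important".

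The intervention is confined to one arm. The schedule in section 10.6 shows it in weeks 1 to 8 for the intervention arm only. Section 9.1 describes the support as open-ended within a nominal 8-week period, and for those who wish to quit during it, "they will be offered 6 weeks of additional behavioural and motivational support from the HT". Not everyone need attend: in the pilot, "participants had an average 4.2 sessions by phone or face to face with the HT with a range of 0-8".

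What controls receive is described in sections 9.2 and 8.8: "Participants allocated to both arms of the trial will receive guidance for smoking reduction and cessation", and "Following randomisation all participants will be sent a letter from CTU confirming which trial arm they have been assigned to, and a guidance sheet". The sheet describes what is available locally.

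SAE information is collected on a different timetable. Under section 15.2 the booklets at months 3 and 9 ask for "the reason for any hospital admission during the past three and six months respectively". Section 10.6 lists self-reported SAEs at both visits without distinction by arm.

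**The concern.** A reporting window should be one that staff can apply to any participant and that gives both arms the same observation time. This one depends on an event that occurs in one arm only, and at a date that depends on how long the participant stayed in contact.

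Three things follow if the rule is applied literally:

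- The same event at the same time since randomisation may have to be reported for one participant and not for another, and the difference is related to arm.
- Events after the window are reported only at the investigator's discretion, in a trial whose participants cannot be blinded.
- Deciding whether an event lies inside the window requires the allocation and the date of last Health Trainer contact. Section 8.8 tries to keep staff who collect follow-up data blind, while sections 15.2 to 15.4 give the local research assistant the task of ascertaining SAE details.

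Under section 20.5 the DMC may advise amending or terminating the trial on grounds of safety, so what it sees should be comparable between arms.

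**Working it through.** The protocol states no SAE rate and no window length in months, so there is no figure of its own to reproduce.

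**1. Where the window ends.** Inputs: 8 weeks of contact and 6 further weeks for those who wish to quit (section 9.1); 4 months after the last intervention (section 15.1.3). One week is 7/30.4375 months.

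Window end = weeks of contact × 7/30.4375 + 4.

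| Last intervention | Window end (month) | Gap to month 9 (months) |
|---|---|---|
| 8 weeks of contact | 1.84 + 4 = 5.84 | 3.16 |
| 14 weeks of contact | 3.22 + 4 = 7.22 | 1.78 |
| Guidance letter at day 0 (assumed anchor) | 0 + 4 = 4.00 | 5.00 |
| Letter not counted as an intervention | undefined | – |

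**2. What the booklets cover.** Recall is 3 months at month 3 and 6 months at month 9. Together that is months 0 to 9, in both arms. The collection period and the reporting period therefore disagree for every participant in the table.

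**3. How unequal the windows could be.** A ratio exists only if controls are given an anchor. Assume the letter at day 0, so 4.00 months for controls.

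- All intervention participants have 8 weeks: 5.84/4 = 1.46.
- All have 14 weeks: 7.22/4 = 1.80. This is the upper bound for the stated durations. It needs every intervention participant to take up the extra 6 weeks at the end of week 8.
- A mixed case: take the pilot's 22% quit attempts in the intervention group (section 5.1.6) as the share with 14 weeks, and 8 weeks for the rest. Then 0.22 × 7.22 + 0.78 × 5.84 = 6.14 months, ratio 1.54.
- As the mixed case, but only 80% engage (the upper progression threshold in section 11) and non-engagers get 4 months: 0.80 × 6.14 + 0.20 × 4 = 5.71 months, ratio 1.43.
- As the mixed case, with 50% engagement: 0.50 × 6.14 + 0.50 × 4 = 5.07 months, ratio 1.27.

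The time between consent and randomisation lies in both arms' windows and would lower each ratio a little. So would participants who attend some sessions but stop before week 8.

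**4. What that means in counts.** Assume an equal and constant SAE rate of 1% per month and 450 per arm; the rate is an assumption. Expected count = 450 × 0.01 × months.

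- Controls, 4.00 months: 18.0.
- Intervention, 5.07 to 6.14 months: 22.8 to 27.6; at the 7.22-month upper bound, 32.5.
- Either arm over a common 9 months: 40.5, ratio 1.00.

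At 2% or 5% per month all counts scale by 2 or 5, and the ratios do not change.

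**The case against.** A reader might infer that the trial's safety comparison is biased, with 1.5 to 1.8 times as many SAEs expected in the intervention arm under no true effect. The documents do not support that, for these reasons:

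- **Capture is symmetrical.** Both arms get the same booklets with the same recall. Section 15.3 asks GPs to report any SAE, without limit by arm. Section 15.2 has the research assistant follow up any admission reported in a booklet, with no window filter. If those hospitalisations are counted, observation is 9 months against 9 months.
- **No restricted comparison is stated.** The protocol describes no between-arm SAE analysis and does not say that tables are limited to the 15.1.3 window. Exposure handling is normally settled in the SAP, which was not available for this check.
- **The ratio rests on assumptions.** It needs a per-participant reading and the letter as the control anchor. The top of the range also needs full contact for everyone.
- **The phrase may mean the last intervention delivered in the whole trial**, which would give one calendar cut-off for both arms.

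The first three points stand, and they make the bias conditional. They do not close the gap. The booklets ask about in-patient episodes, so deaths outside hospital and disability depend on other routes. Section 10.4 expects only 60–65% to complete month 3. For what the booklets miss, the 15.1.3 window decides what must be reported.

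The fourth point is strained. With 12 months of recruitment (section 17.2.5), the first recruits would be reportable until 12 + 5.84 = 17.8 to 12 + 7.22 = 19.2 months. Section 10.5 caps participation at 15 months, and section 10.7 ends it at 9 for most.

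**Conclusion.** The rule cannot be applied as written. Its anchor is undefined for controls and for intervention participants with no session, moves between about month 5.8 and month 7.2 within the intervention arm, and conflicts with the month 0–9 collection in sections 15.2 and 10.6. That much rests on the text alone.

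Unequal reportable time is a possible consequence and not an established one. If counts follow the window per participant, with the letter at day 0 as the control anchor and partial engagement, the intervention arm would have about 1.3 to 1.5 times the control arm's time. The DMC's safety data could then be biased against the intervention, and reporting of later events would be discretionary. Equal booklet capture of hospitalisations limits this. The primary outcome, its analysis and the sample size are not affected.

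**What to change.** Reconcile section 15.1.3 with sections 15.2 and 10.6. Replace the intervention-based end point with one fixed window, starting at consent (or randomisation) and applying identically to every participant in both arms. The natural end is the 9-month assessment, because the booklets already cover the time up to it. Reporting can then be decided without knowing the allocation or the date of last contact.

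The cost is one amended sentence and some additional SAE forms. At the assumed 1% per month, events between the illustrative window ends and month 9 would number about 40.5 − 18.0 = 22.5 in controls and 40.5 − 25.7 = 14.8 in the intervention arm (25.7 = 450 × 0.01 × 5.71, the 80% engagement case). Hospital admissions among them that appear in the 9-month booklet are already to be followed up under section 15.2.

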15.2 Serious adverse event self- reporting at 3 and 9 months

The questions in the self-completion study questionnaire booklets ask participants to record the number of in-patient episodes within a set recall period. At the 3 and 9 month time points, participants are asked to record if they have been hospitalised, the reason for any hospital admission during the past three and six months respectively and whether they think that the hospitalisation was related to participation in this study. On receipt of a questionnaire indicating a past hospital admission, the CTU will liaise with the relevant local RA who will be responsible for ascertaining further details about the SAE from the participant and/or GP records as appropriate.

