10.4 Loss to follow-up

Based on the data from the TARS pilot study (EARS) [1] it is anticipated that 60-65% of TARS participants will complete follow-up at 3 months.

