10.6 Schedule of delivery

	Screening &	Day	Intervention	Month	Month	Month
	Baseline	0	Week 1 – 8*	3	9	15
			(Intervention			
			arm only)			
Eligibility check	Х					
Consent	Х					
Randomisation		Х				
Demographics	Х					
Importance and confidence in smoking reduction and	Х			Х		
cessation						
Importance and confidence in being physically active	Х			Х		
Availability of support to reduce smoking and increase	Х			Х		
physical activity						
Use of physical activity for smoking regulation	Х			Х		
Self-reported physical activity (7-day physical activity	Х			Х	Х	
recall)						
Planning to change smoking	Х			Х		
Planning to change physical activity	Х			Х		
Self-monitoring of smoking	Х			Х		
Self-monitoring of physical activity	Х			Х		
Urge & strength of urge to smoke	Х			Х		
Use of e-cigarettes and NTR (nicotine replacement	Х			Х	Х	Х
therapy) products						
Health related quality of life (EQ-5D-5L & SF12)	Х			Х	Х	
Self-reported weight & height (BMI)	Х			Х	Х	
Health service utilisation and costs,	Х			Х	Х	
Serious adverse events (self-reported)				Х	Х	
Self-reported prolonged abstinence (since quit attempt,				Х	Х	Х
with date, if relevant)						
CO expired air confirmed abstinence (<10ppm)**				Х	Х	Х
Accelerometer (7 days)				Х		

^{*}If a smoker wishes to quit at any time during the 8 week intervention period, they will be offered 6 weeks of additional support from the Health Trainer, a meeting with a specialist advisor in a stop smoking service, and pharmacological and behavioural support.

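### A participant who skips the 3-month booklet is never asked about hospital admissions in months 0-3, because the 9-month recall stays fixed at six months

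*Protocol*

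**What the plan says.** Protocol section 15.2 relies on booklet questions that ask participants to "record the number of in-patient episodes within a set recall period", and at 3 and 9 months for "the reason for any hospital admission during the past three and six months respectively". The research assistant's enquiry begins "On receipt of a questionnaire indicating a past hospital admission". The schedule in section 10.6 marks self-reported SAEs at months 3 and 9 only, and section 16.6 says that questionnaire data will not be queried with participants.

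Section 15.1.3 sets the reporting duty: "SAEs will be reported from the time of consent until 4 months after the last trial intervention". It adds: "If an unreported event from this time period is identified at a later date, retrospective reporting must occur immediately".

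On response, section 10.4 states that "it is anticipated that 60-65% of TARS participants will complete follow-up at 3 months". Section 13 provides for chasing: "Up to two reminder letters will be issued to remind participants to return the questionnaire booklets".

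There are other capture routes. Section 15.3 has a letter asking each participant's GP to tell the trials unit of any SAE. Section 15.4 accepts reports from patients, relatives or other channels. Section 14.2 has participants monitored for adverse events and changes in health at each counselling session.

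**The concern.** The recall periods are fixed lengths, not intervals anchored to randomisation or to the last completed booklet. They tile months 0-9 only for someone who completes both booklets on time. The protocol expects more than a third of participants not to complete the first one, and it gives no instruction to extend the second question for them.

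The unasked months are those in which the intervention arm is being supported to become more active. They are therefore the months of most interest for any activity-related admission, and they fall within the period for which section 15.1.3 requires reporting. If events there are picked up less completely, the SAE counts seen by the data monitoring committee and in the final report may be too low. Because one of the back-up routes exists in one arm only, the completeness of capture may also differ between arms, which would weaken a between-arm safety comparison.

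**Working it through.** The protocol states no figure for SAE coverage, so there is none to reproduce. The check is interval arithmetic on the recall windows.

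**Inputs**
- Recall of 3 months at the 3-month booklet and 6 months at the 9-month booklet (section 15.2).
- Expected 3-month completion of 60-65% (section 10.4), and a 50% floor below which the study may not progress (section 11).
- 900 participants, 450 per arm (section 4).
- Intervention of 8 weeks, with 6 further weeks of support if the smoker decides to quit within that time, so at most 14 weeks (section 9.1).
- SAE reporting until 4 months after the last intervention (section 15.1.3).
- Conversion: 52.18 weeks = 12 months, so 8 weeks = 1.84 months and 14 weeks = 3.22 months. The intervention is assumed to start at randomisation.

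**Coverage.** With completion at months t3 and t9, the months asked about are [t3 − 3, t3] together with [t9 − 6, t9].
- Both on time (t3 = 3, t9 = 9): 0-3 and 3-9, so there is no gap.
- 3-month booklet missing, 9-month on time: 3-9 only, so months 0-3 are unasked.
- 3-month booklet missing, 9-month one month late, counting back from completion: 4-10, so months 0-4 are unasked.

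**What months 0-3 contain**
- Standard course: all of the 8 weeks (1.84 < 3).
- Longest course: 3 / 3.22 = 93%. The remainder falls inside the on-time 9-month window.
- Share of the post-randomisation reporting window: 3 / (1.84 + 4) = 3 / 5.84 = 51% for an 8-week course, and 3 / (3.22 + 4) = 3 / 7.22 = 42% for a 14-week course.

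**How many give no 3-month report**
- 65% completion: 900 × 0.35 = 315, about 158 per arm.
- 60% completion: 900 × 0.40 = 360, 180 per arm.
- 50% floor: 900 × 0.50 = 450, 225 per arm.

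Per-arm figures assume equal non-response in the two arms.

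**How many of these the 9-month wording affects.** This is the number who skip month 3 but return month 9. The protocol does not give that share. Assuming 20-50% purely for illustration: 315 × 0.20 = 63 to 360 × 0.50 = 180 participants.

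**Late 3-month return**, if recall is counted back from completion:

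| Delay (months) | Window asked | Unasked | Share of the 8 weeks unasked |
|---|---|---|---|
| 0.5 | 0.5-3.5 | 0-0.5 | 0.5 / 1.84 = 27% |
| 1 | 1-4 | 0-1 | 1 / 1.84 = 54% |
| 2 | 2-5 | 0-2 | 100% |

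The gap equals the delay. Section 13 provides for reminders but states no interval, so these delays are assumptions.

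**The case against.** A reader might infer that admissions in months 0-3 are lost for these participants. The protocol does not support that. The GP letter goes out whether or not a booklet comes back, other reports are accepted, and an event identified late must still be reported. Such admissions are not asked about by questionnaire, but they are not excluded from capture.

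A reader might also infer that the booklet is the only organised SAE collection. Section 14.2 shows otherwise: session monitoring is repeated contact during the intervention, in the arm that receives the activity support. It does not close the gap. Controls have no sessions, and in the pilot the number attended ranged from 0 to 8 with an average of 4.2 (section 9.1). The GP route relies on the GP becoming aware and making contact. The duty of retrospective reporting applies once an event is identified, but it does not find one.

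A third tempting reading is that late return leaves the whole intervention period unasked. In general it does not: the gap is only as long as the delay. Even that depends on recall running from the date of completion, and the booklet's wording is not shown.

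Finally, the arithmetic counts people, not missed events. The protocol gives no admission rate and no GP notification rate, so the effect on SAE totals cannot be estimated. Non-responders at 3 months who also skip month 9 gain nothing from a reworded question. These limits stand. They restrict the size of the point but not the defect: the 9-month question has no catch-up.

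**Conclusion.** The point holds for participants who miss the 3-month booklet and return the 9-month one. On the protocol's own forecast 35-40%, or 315-360 of 900, give no 3-month report. For those who answer at 9 months, three months go unasked. Those months contain the whole standard intervention and, for an 8-week course, about half of the post-randomisation SAE reporting window. Ascertainment there rests on passive notification, plus session monitoring in one arm only.

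The consequence is possible under-ascertainment of SAEs and possibly different back-up capture by arm. It is not a demonstrated loss of events, and the primary outcome is unaffected. The number affected depends on the 9-month response among 3-month non-responders, which is not stated; 63-180 is illustrative only. Late return is a secondary, conditional gap equal to the delay. The amendment is worth making because the gap follows from a stated rule and is cheap to close.

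**What to change.** In section 15.2 and the booklets, replace the fixed recall for SAE purposes with an anchored item:
- 3-month booklet: any hospital admission, with its date, since joining the study.
- 9-month booklet: any hospital admission, with its date, since joining the study or since the last completed booklet. The trials unit could pre-print the anchor date.
- De-duplicate repeat reports by admission date.

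Keep this as a separate SAE item. Hospital admission is also a resource-use question feeding the 9-month cost profile (sections 19.1 and 19.2), and those recall periods should stay as they are.

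For a participant who skips month 3 and returns month 9, the self-report gap falls from 3 months to 0. The costs are one extra or reworded item in two booklets, a short edit to section 15.2, recall of up to 9 months for 3-month non-responders, and minor de-duplication work. Participants who return neither booklet still depend on the other routes.
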